All MS participants will undergo the following procedures: I. Participants will be asked to refrain from eating for 2 hours prior to their arrival at our center. Once here, after the consenting process is finished, participants will have their temperature taken aurally (two measurements will be taken for reliability) and will then complete a simple motor task, the hand dynamometer test (5 measurements will be taken), an objective measure of physical fatigue that has been used in MS (Greim et al, 2007). They will then have their aural temperature measured again, before filling out questionnaires on fatigue (FSS, VAS), mood (BDI-II), and a diary page. Aural temperature will be recorded once again, just before the pill is administered (placebo or aspirin). II. Scan condition: Participants are then scanned for one hour. Immediately after scanning, aural temperature is recorded, followed by the same set of questionnaires, plus one additional questionnaire, the Global Fatigue Change (GFC). All participants will also be asked which pill they think they received, aspirin or placebo. The hand dynamometer test will be completed once again, followed by a final aural temperature measurement. All of these procedures are expected to take under 2 hours. III. Patients who are not scanned will wait quietly for one hour, and then baseline procedures will be repeated [temperature taken aurally (two measurements will be taken for reliability), repeat the hand dynamometer test, complete questionnaires on fatigue (FSS, VAS)]. Exercise condition: Ten RRMS patients will be randomized in a crossover double-blind study. After undergoing same procedures as above (section I), each subject in the exercise condition will undergo the following additional procedures: subject will have peak ventilatory capacity (Maximum Voluntary Ventilation, MVV) determined before the exercise test via a Vmax Encore System (CareFusion Corp, San Diego, CA). Each subject will have a 5-minute resting phase followed by a three-minute warm up and then a progressive ramped exercise test using a VIA Sprint 150P lower body cycle ergometer (CareFusion Corp, San Diego, CA) until achieving one of the following VO₂max criteria: respiratory exchange ratio (RER) 1.1, increases in ventilation without concomitant increases in VO₂, maximum age predicted heart rate and/or volitional fatigue. An individualized ramping protocol will be used as determined by weight and subject's exercise profile as determined by a certified exercise physiologist. Blood pressure, tympanic temperature, and RPEbr and RPElegs data will be collected at 3-minute intervals. Minute ventilation, expired oxygen (O₂), carbon dioxide (CO₂), watts, RER, and total time will be measured using Vmax Encore Metabolic system (Sensormedics, Inc, Loma Linda, CA). Flow sensor and gas analyzer will be calibrated against known medical grade gases before each test. VO₂max will be determined from peak 20-second average of the breath-by-breath measurement of VO₂. Identical test procedures will be carried out after initiation of placebo or ASA. Anaerobic threshold will be determined for each subject using the V-slope technique. The exercise test will commence one hour after pill was administered. Exercise test: Patients will maintain a cycle cadence between 50-60 revolutions per minute (RPM) on the lower body cycle ergometer for the duration of the test. The test will be terminated when the cadence drops below 40 RPM for 5 seconds, or when participant reaches volitional exhaustion [i.e., in the presence of American Thoracic Society (ATS) standard test termination criteria]. In healthy adults, the estimated time to bring about volitional exhaustion is 8-12 minutes. At termination, RPEbr, RPEleg, blood pressure (BP), and tympanic

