Exercise condition: 10 RRMS patients will serve in the exercise condition to investigate the effect of aspirin/placebo on exercise performance. Patients will be scheduled to come in for two separate sessions, separated by at least one week. After undergoing all no-scan condition procedures as detailed above, participants will be familiarized with Borg's ratings of perceived exertion (RPE) CR10 scale for breathing (RPEbr) and legs (RPEleg) to be completed during and after the exercise session. Exercise sessions: The Human Performance Laboratory is staffed with ACLS and BCLS (basic and advanced cardiac life support) qualified personnel. Exercise tests will be conducted by a certified exercise physiologist who will be accompanied by a physician to ensure safety. All exercise testing equipment is current and certified for use with human subjects. Cardiopulmonary exercise testing is performed using a Carefusion Encore 29 metabolic system (Viasys Healthcare, San Diego, CA). Echocardiogram (ECG) monitoring is done with a twelve lead system attached to the Encore 29 with cardiosoft software (Viasys, Yorba Linda, CA). Maximum aerobic fitness (VO₂max) will be measured by a graded exercise test on an Ergoline 150P electronic-braked cycle ergometer (Carefusion, San Diego, CA). Each subject will have peak ventilatory capacity (Maximum Voluntary Ventilation, MVV) determined before the exercise test via a Vmax Encore System (Carefusion, San Diego, CA). Each subject will have a 5-minute resting phase followed by a three-minute warm up and then a progressive ramped exercise test until achieving one of the following VO₂max criteria: respiratory exchange ratio (RER) 1.1, increases in ventilation without concomitant increases in VO₂, maximum age-predicted heart rate and/or volitional fatigue. An individualized ramping protocol will be used as determined by weight and subject's exercise profile as determined by a certified exercise physiologist. Blood pressure, tympanic temperature, and RPEbr and RPElegs data will be collected at 3-minute intervals. Minute ventilation, expired oxygen (O₂), carbon dioxide (CO₂), watts, RER, and total time will be measured using Vmax Encore Metabolic system (Carefusion, San Diego, CA). Flow sensor and gas analyzer will be calibrated against known medical grade gases before each test. VO₂max will be determined from peak 20-second average of the breath-by-breath measurement of VO₂. Identical test procedures will be carried out after Initiation of placebo or ASA (double blind will be maintained). Anaerobic threshold will be determined for each subject using the V-slope technique. Exercise test: Patients will maintain a cycle cadence between 50-60 revolutions per minute (RPM) for the duration of the test. The test will be terminated when the cadence drops below 40 RPM for 5 seconds, or when participant reaches volitional exhaustion [i.e., in the presence of American Thoracic Society (ATS) standard test termination criteria]. In healthy adults, the estimated time to bring about volitional exhaustion is 8-12 minutes. At termination, RPEbr, RPEleg, blood pressure (BP), and tympanic temperature (right ear) will be recorded. In addition, participants will record their current level of fatigue with VAS of fatigue and Global Fatigue Change. Each exercise session will be

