
performed at the same time of day (± 1 hour), and between the hours of 10 am and 5 pm. The temperature of the room will be held constant to within ± 5 degrees Fahrenheit, and recorded at the start of each session.

In addition, we will recruit 30 RRMS patients into a "no-scan" condition in which they will undergo all study procedures except the scan.

All participants will be asked at the end of their session(s) whether they think they received aspirin or a placebo, to ensure effectiveness of blinding.

Biological Specimens

Add an individual entry for each human specimen type that will be collected or utilized for the proposed study. For each specimen type, indicate the source or sources from which you will obtain the specimens.

The use of specimens for research purposes may require that informed consent (or a waiver, if applicable) and HIPAA Authorization (or a waiver, if applicable) be obtained from subjects.

Type:

Urine

Source:

From Columbia and/or NYP Subjects/Patients or Repositories managed by Columbia

Select all that apply to this specimen type:

Specimens will be prospectively collected specifically for this research.

Residual specimens from clinical care that would otherwise be discarded have been or will be collected.

Specimens to be analyzed will be (or have been) collected from a commercial source.

Specimens to be analyzed will be (or have been) collected under a separate CU IRB-approved protocol; this could be an approved research repository protocol.

From Non-Columbia/NYP Subjects/Patients or Repositories not managed by Columbia

Description of Specimen and Method of Obtaining:

Urine Pregnancy test

Indicate the manner in which the specimens will be labeled:

Specimens will be labeled with direct identifiers

Specimens will be labeled with a code and the research team has the key and can link specimens to direct identifiers.

This code would be considered an indirect identifier

The identifiers will be removed prior to the receipt of the specimens by Columbia researchers and no link will remain

Specimens were originally collected without identifiers

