If you select the Abbreviated Submission checkbox and a section is not covered by the attached stand-alone protocol, you will need to go back and provide this information in your submission.

Potential Risks:

Provide information regarding all risks to participants that are directly related to participation in this protocol, including any potential for a breach of confidentiality. Risks associated with any of the items described in the Procedures section of this submission should be outlined here if they are not captured in a stand-alone protocol. Risks of procedures that individuals would be exposed to regardless of whether they choose to participate in this research need not be detailed in this section, unless evaluation of those risks is the focus of this research. When applicable, the likelihood of certain risks should be explained and data on risks that have been encountered in

past studies should be provided.

Abbreviated Submission - This information is included in an attached stand-alone protocol. Proceed to the next question

The risks posed by the methods used in this study are very small. Three trials of aspirin to reduce fatigue in RRMS has been conducted previously, with no adverse events noted. In addition, our study physician, [name] will work closely during recruitment to ensure that there are no counter indications to one-time aspirin use for any participants. Regarding the MRI/fMRI, the main risk is related to the presence of metal within the body (e.g. non-MRI compatible aneurysm clips, metal shards in the body or eyes, or recently placed surgical hardware) or electronic devices (e.g. pacemaker, cochlear implant). Because the risks of MRI/fMRI to fetuses are believed to be minimal, but are nevertheless not known, females will be given a pregnancy test on the day of the MRI/fMRI scan, and if pregnant will be excluded from the study. In general, participants may experience anxiety or claustrophobia while confined in the small space of the magnet. Participants will be briefed in detail about what they will experience during the scanning session. This should reduce problems related to anxiety or claustrophobia. The scanner is very loud, so participants will be given headphones and earplugs. Participants will be able to be heard by the scanner operator at all times, and will be given a 'panic' button to push at any time in order to be removed from the scanner.

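### The only timed pregnancy test and the only pregnancy exclusion are tied to the MRI scan day, so as most naturally read they miss the 40 no-scan and exercise patients, who also take the pill

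*Combined protocol and SAP*

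**What the plan says.** All references are to the combined protocol and SAP.

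- **Potential Risks** holds the one operative rule: "females will be given a pregnancy test on the day of the MRI/fMRI scan, and if pregnant will be excluded from the study". The reason given is that "the risks of MRI/fMRI to fetuses are believed to be minimal, but are nevertheless not known". The same section has the study physician work during recruitment "to ensure that there are no counter indications to one-time aspirin use for any participants".
- **Study design narrative, section I**, applies to all MS participants and ends with the pill, aspirin or placebo. Section II covers the scan. Section III says: "Patients who are not scanned will wait quietly for one hour, and then baseline procedures will be repeated". No pregnancy test appears in any of the three.
- **Procedures** describes "30 RRMS patients into a 'no-scan' condition in which they will undergo all study procedures except the scan". The exercise patients start the same way, "After undergoing all no-scan condition procedures as detailed above", and attend two sessions at least a week apart, each with a ramped cycle test.
- **Biological Specimens** lists a "Urine Pregnancy test" with no timing, condition or consequence.
- **Subject Population Justification** and the expanded exercise exclusions in Potential Risks do not mention pregnancy.
- **Subjects** answers No to the question whether pregnant women are targeted.

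**The concern.** The plan tests women before a scan whose fetal risk it believes to be minimal, because that risk is not known. It does not clearly apply the same precaution before the study drug or the ramp test, which are the only study exposures of this kind for the patients who are not scanned. Staff who follow the text as it most naturally reads could give the pill, and in the exercise condition a maximal exercise test, to a woman whose pregnancy nobody has recognised. What is at stake is participant safety and the clarity of the instructions. No endpoint, estimate or test in the analysis plan depends on it.

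**Working it through.** **Step 1: every mention of pregnancy in the available text.**

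| Place | What it gives | Timing | Who | Consequence |
|---|---|---|---|---|
| Potential Risks | Test, justified by MRI | Day of scan | Females with a scan day | Exclusion |
| Biological Specimens | Urine test listed | None | Not stated | None |
| Subjects, vulnerable populations | Not targeted | – | – | None |

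It is absent from the visit steps in the study design narrative, the scan, no-scan and exercise text under Procedures, the expanded exercise exclusions, and the inclusion/exclusion criteria. The form also says that no external protocol describes all the procedures, so no such document is available to fill the gap.

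**Step 2: reproduce the plan's enrolment figure.** The Subjects table gives 20 scan, 30 no-scan and 10 exercise patients, with 12 healthy controls.

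- MS patients: 20 + 30 + 10 = 60, as stated.
- Total: 60 + 12 = 72, as stated.

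**Step 3: count those who take a pill without a scan day.**

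- Patients: 30 + 10 = 40 of 60 (67%).
- Pill visits: 20 + 30 + (10 × 2) = 70, of which 30 + 20 = 50 have no scan.
- Ramp tests: 10 × 2 = 20, none on a scan day.

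**Step 4: can a change still reach them?** The table shows 10 of the 60 enrolled, condition not stated. Even if all 10 came from the no-scan and exercise conditions, 40 − 10 = 30 of these patients are still to come.

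**Step 5: which reading fits better?** The wording on no-scan procedures could carry the urine test over to these patients, and the exercise text would then carry it on. Against that, the only sentence that says when and why the test is done makes it a precaution for the scan. Taking away the scan takes away both its reason and its day. The omission from the visit steps adds little, because those steps also leave the test out for scanned women, who are to have it.

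**Step 6: do other safeguards cover the gap?** The physician's check for aspirin contraindications takes place during recruitment, does not name pregnancy and specifies no test. Contraindications to stress testing are judged by chart review or physician consultation, and a physician attends the exercise tests. These may catch a known pregnancy. They would not be expected to catch an unrecognised one, and for scanned women the plan did not rely on them alone.

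**The case against.** The strongest reply has four parts.

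1. *The test may already cover everyone.* The Procedures section asks for all study procedures, gives no-scan patients everything but the scan, and then lists the urine test with no condition attached. A urine test is not the scan, and the rule in Potential Risks excludes a pregnant woman from the whole study, not just from scanning. This stands as far as it goes: the text is ambiguous. It does not settle the matter, because nothing tells staff when to test a patient who has no scan day, or what to do with the result.

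2. *Different exposures can have different precautions.* Aspirin is entered as an approved drug used within its labelling, and it has its own physician check. This limits the argument to one of internal consistency. The documents give no fetal risk for a single 650 mg dose or for a ramp test, so nothing can be said about the size of any harm.

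3. *Unseen material may say more.* The consent forms (one specific to exercise), the drug insert and a few pages of the form were not available. That is a real limit on the finding.

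4. *The count of 40 includes men and women past childbearing age.* True. The criteria allow ages 18 to 65 and give no split by sex, so the number of women who could be pregnant is unknown.

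A reader might infer that 40 patients will go untested, that pregnant women will be given aspirin, or that the study has no pregnancy safeguard outside the scanner. The documents support none of these. They show a rule whose reach is not stated.

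**Conclusion.** The point holds for the text available. The only timed test and the only exclusion for pregnancy are a scan-day MRI precaution. As most naturally read, neither applies to 40 of the 60 patients who take a pill (50 of 70 pill visits and all 20 ramp tests). The contrary reading makes the text ambiguous but does not repair it. The conclusion assumes that the unseen consent forms, drug insert and missing pages do not extend the rule, and that the 40 include some women who could be pregnant, which is likely at the permitted ages but not quantified. It is a cheap improvement to participant safety, with no claim about the size of harm and no effect on any analysis. Confidence is medium.

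**What to change.** 1. Add pregnancy as an exclusion for all MS conditions in Subject Population Justification, and to the expanded exercise exclusions in Potential Risks.
2. Reword the sentence in Potential Risks, and add a step to section I of the study design narrative, so that females in every MS condition have the listed urine test on the day of the visit, after consent and before the pill. If it is positive: no pill, scan or ramp test. Keep the group as females, as the present rule does; restricting it to women of childbearing potential would narrow the existing safeguard. Keep the scan-day test for female healthy controls, who are scanned but take no pill.
3. Name the conditions in the Biological Specimens entry.
4. As a secondary step, apply the same rule at the second exercise session, which is at least a week after the first.

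Placing the test before the pill also helps scanned women, since the present wording fixes the day but not the order. If the investigators already intend the test for every condition, the change is wording only.

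**Cost.** At most 30 + 20 = 50 extra urine tests, reached only if all 40 patients were female and none had yet been seen (30 + 10 = 40 without the repeat at session 2), and a few minutes per visit. A positive result at session 2 would lose one of the 10 crossover pairs, taking the planned t test from 10 − 2 = 8 to 9 − 2 = 7 degrees of freedom. Such a patient should be reported as withdrawn, with the reason.

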
temperature (right ear) will be recorded (BODY TEMP 2). In addition, participants will record their current level of fatigue with VAS of fatigue and Global Fatigue Change (GFC). Each exercise session will be performed at the same time of day (± 1 hour), and between the hours of 11 am and 5 pm. The temperature of the room will be held constant to within ± 5 degrees Fahrenheit, and recorded at the start of each session. After each phase (placebo and ASA), participants will be asked which condition they think they were in, to ensure effectiveness of blinding. A sample of 12 healthy controls will be enrolled to obtain normative brain temperature. The HC group procedures will be as follows: After being consented, participants will fill out a BDI-II, FSS, VAS, and a diary page. They will have aural temperature measured before being scanned. After the scan, aural temperature will be measured once again, before participants are asked to fill out questionnaires once again: FSS, VAS, GFC. These procedures are expected to take approximately one hour total.

Statistical Procedures:

Provide sufficient details so that the adequacy of the statistical procedures can be evaluated including power calculations to justify the number of participants to be enrolled into the study. Definitions of subject terms such as enrolled and accrued as used for Rascal submissions can be found in the Subjects section.

[] Abbreviated Submission - This information is included in an attached stand-alone protocol. Proceed to the next question

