Scan condition: 20 RRMS patients will serve in the scan condition. All participants will be asked to refrain from eating 2 hours prior to their scheduled appointment. Participants will be scanned with MRS to derive brain temperature; fatigue will be measured with validated self-report fatigue questionnaires (FSS 46) and body temperature will be measured with an aural thermometer (Braun ThermoScan IRT 4520 Aural thermometer, consistent with our prior studies^{23,24}) immediately prior to scanning. We hypothesize that higher brain temperature in RRMS patients is correlated with worse fatigue. 10 patients will be randomized to aspirin group (standard dose, 650 mg in 1 pill), and 10 patients to placebo (placebo, 650 mg in 1 pill). After being administered aspirin/placebo, patients will have temperature measured aurally and then receive a scan. We hypothesize that brain temperature will decrease in the aspirin group compared to the placebo group. As a secondary outcome, we will examine change in fatigue after aspirin/placebo administration to see whether the aspirin group experienced a greater decrease in fatigue than placebo group. 12 healthy controls will be enrolled to obtain normative brain temperature. These subjects will fill out questionnaires, have temperature taken aurally, and receive a scan. After scanning, aural temperature will be measured and questionnaires filled out. All subjects will receive only 1 scan and only RRMS subjects will be randomized.

All MRIs will be read by study personnel for research purposes, and will also be read by a trained radiologist to screen for the presence of any IFs (incidental findings). If the radiologist sees an IF on a scan, the research team will contact the study subject immediately.

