The alternative to participating in this study is to not participate in this study.

Data and Safety Monitoring:

Describe how data and safety will be monitored locally and, if this is a multi-center study, how data and safety will be monitored across sites as well.

Abbreviated Submission - This information is included in an attached stand-alone protocol. Proceed to the next question

Data and safety will be monitored to identify unanticipated problems by providing all enrolled subjects with contact information for the study coordinator and the study PI. In addition, over the intervening 3 years between baseline and follow-up, all subjects will be periodically contacted to ensure follow-up participation (i.e., reduce attrition). This contact will also provide study personnel the opportunity to monitor unanticipated problems.

Subjects

Unless otherwise noted, the information entered in this section should reflect the number of subjects enrolled or accrued under the purview of Columbia researchers, whether at Columbia or elsewhere.

Target enrollment:

72

Number enrolled to date:

11

Does this study involve screening/assessment procedures to determine subject eligibility?

No

Is this a multi-center study?

No

Does this study have one or more components that apply to a subset of the overall study population (e.g. Phase 1/2, sub-studies)?

Yes

Name/Procedure	Target enrollment	Enrolled to date	Enrollment Status
Aspirin Experiment	60	10	Open to enrollment or ongoing review of records/specimens
	Addition Information: 20 in the scan condition, 30 in the no-scan condition, 10 in the exercise condition		
Healthy controls	12	1	Open to enrollment or ongoing review of records/specimens

Vulnerable Populations as per 45 CFR 46:

Will children/minors be enrolled

No

Will pregnant women/fetuses/neonates be targeted for enrollment?

No

Will prisoners be targeted for enrollment?

No

Other Vulnerable Populations:

- Individuals lacking capacity to provide consent
- CU/NYPH Employees/Residents/Fellows/Interns/Students
- Economically disadvantaged
- Educationally disadvantaged
- Non-English speaking
- Other Vulnerable populations
- None of the Populations listed above will be targeted for Enrollment

Subject Population Justification:

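### The only staff-initiated contact in the safety-monitoring section rests on a 3-year follow-up that the one- or two-session study does not describe

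*Combined protocol and SAP*

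**What the plan says.** The Data and Safety Monitoring field names two measures for finding unanticipated problems.

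- The first is "providing all enrolled subjects with contact information for the study coordinator and the study PI".
- The second is contact by staff: "over the intervening 3 years between baseline and follow-up, all subjects will be periodically contacted to ensure follow-up participation". The field then adds: "This contact will also provide study personnel the opportunity to monitor unanticipated problems".

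The visits are described in the study design text and the Procedures section.

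- **Scan condition:** "All of these procedures are expected to take under 2 hours", and "All subjects will receive only 1 scan and only RRMS subjects will be randomized".
- **No-scan condition:** "Patients who are not scanned will wait quietly for one hour, and then baseline procedures will be repeated".
- **Healthy controls:** "These procedures are expected to take approximately one hour total".
- **Exercise condition:** "Patients will be scheduled to come in for two separate sessions, separated by at least one week".

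The last thing asked of any patient is a guess at the pill received, at the end of the session or sessions. The form answers No when asked whether an external protocol covers all procedures, and the procedures field is meant to be complete.

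**The concern.** The monitoring field is the study's operative plan for detecting problems. Of its two measures, only the second has staff approaching subjects, and it depends on an interval and a follow-up visit that appear nowhere else. If the described visits are right, that measure cannot operate as written.

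What is at stake is the record of harms. Sixty patients are planned for the aspirin experiment, and ten of them have two ramped exercise tests each. If nobody is assigned to ask about events, a report of none could mean that none occurred or that nobody asked, and the reader could not tell which. This applies most to anything that arises after a patient leaves the last session.

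**Working it through.** No power, alpha or sample-size figure is involved, so the check compares the monitoring field with every description of a visit.

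**Step 1. Count sessions per subject.**

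| Group | Planned n | Sessions described | Source |
|---|---|---|---|
| Scan, RRMS | 20 | 1 (under 2 hours) | Study design; Procedures |
| No-scan, RRMS | 30 | 1 (repeat after an hour) | Study design; Procedures |
| Healthy controls | 12 | 1 (about an hour) | Study design; Procedures |
| Exercise, RRMS | 10 | 2 (at least a week apart) | Procedures |

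The total is 20 + 30 + 12 + 10 = 72, which matches the target enrollment in the Subjects section.

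- One session: 20 + 30 + 12 = 62 of 72.
- Two sessions: 10 of 72.
- Follow-up at 3 years: described for 0 of 72.

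The gap between exercise sessions has a minimum and no stated maximum. That does not create a 3-year interval, and the monitoring sentence speaks of all subjects, not the exercise patients alone.

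**Step 2. Look for a follow-up elsewhere.** The comparisons in Statistical Procedures are cross-sectional, before against after a pill, or between the two exercise sessions. None uses later data. The aims name no longitudinal outcome. Compensation is $25 for scan and no-scan patients and $50 for exercise patients, with no payment for follow-up.

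**Step 3. Look for adverse-event collection at the sessions.** The listed measurements are ear temperature, hand dynamometer, fatigue and mood questionnaires, visual analogue scales, a diary page, the global fatigue change rating and the pill guess. The exercise sessions add cardiopulmonary measurements and exertion ratings. None is described as an adverse-event enquiry, and Statistical Procedures contains no safety listing.

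**Step 4. Set out the oversight described outside the monitoring field.**

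- Exercise tests: a physician and a certified exercise physiologist, staff trained in life support, twelve-lead monitoring, blood pressure every 3 minutes, and physician review of the stress tests (Procedures; Potential Risks).
- Scans: an operator who can hear the subject, an alarm button, and a radiologist's read for incidental findings (Potential Risks; Procedures).

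All of this belongs to the test or the scan. None of it is contact after the last session, and none specifies recording of adverse events by treatment.

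**Step 5. Combine.** Without the 3-year contacts, the monitoring field retains one measure, the contact details. Exercise patients do meet staff again at their second session, but no enquiry about the interval is described there.

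**Numbers exposed.** There are 60 patients in the aspirin experiment and 10 × 2 = 20 exercise tests. Enrollment stands at 11 of 72 (10 patients, 1 control), so a correction now would cover 72 − 11 = 61 subjects, of whom 60 − 10 = 50 are patients.

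**The case against.** The strongest reply is that the sentence is probably text carried over from another study and that real safety oversight sits elsewhere. The carry-over is plausible. The data-security text also describes cognitive test data, while the Procedures section answers No to cognitive testing. It remains an inference, and a carried-over sentence still leaves the operative field without a workable active measure.

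The point about oversight elsewhere does stand, and it limits the finding. Several stronger readings are tempting, and the documents do not support them.

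- *Half of the safety monitoring is lost.* One of two measures in a single field is affected. The exercise and scan safeguards lie outside that count.
- *Events are captured only if the subject calls.* Events during an exercise test or scan occur under direct observation. Scan and no-scan patients also remain for about an hour after the pill and are then reassessed. Sole reliance on the subject applies after the last session.
- *No adverse-event question exists.* The diary page and questionnaires are attached to the submission, but their contents are not available for review. One of them may contain such an item.
- *The earlier aspirin trials noted no events because none were sought.* The Potential Risks field reports only that none were noted. It does not say how they were looked for.
- *The study fails to compare safety between arms.* No aim calls for that comparison. With 10 against 10 in the scan condition and 10 patients in the crossover, it would show little even with full capture. A descriptive listing is all that can reasonably be asked.

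**Conclusion.** The contradiction is real and internal to the document. The monitoring field's only staff-initiated measure depends on a 3-year follow-up that is described for none of the 72 subjects. As a result, the field leaves only subject-initiated reporting after the last session, and no described procedure provides systematic adverse-event enquiry or recording at the sessions.

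The finding concerns the completeness of the harms record. It does not show that subjects are unobserved during tests or scans. It also does not touch sample size, alpha or the efficacy analyses.

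It rests on two assumptions: that the procedures field is complete, as the form requires, and that the diary page and questionnaires contain no adverse-event item. If the second is wrong, the plan should say so, and the gap narrows to the period after the last session. The change should be made, but it does not threaten the study's conclusions on efficacy.

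**What to change.** 1. Reconcile the Data and Safety Monitoring field with the visit structure. Either remove the 3-year text or describe the follow-up it assumes: who is contacted, when, and what is asked. The documents do not settle which was intended, so the sponsor must.
2. Tie monitoring to contacts that already exist. Ask about and record adverse events at the end of each session and, for exercise patients, at the start of the second session, so that the interval after the first is covered.
3. Add a line to Statistical Procedures saying that these events will be listed descriptively by treatment received, with no formal test.
4. If the diary page or a questionnaire already asks about adverse events, cite it in the monitoring field.

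The cost is one paragraph and a short form, with no extra visits or staff. No change to dosing, stopping or clinical care is proposed.
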